ASAS=Ankylosing SpondyloArthritis International Society, ASDAS=AS disease activity score, ASQoL=ankylosing spondylitis quality of life, BASDAI=Bath ankylosing spondylitis disease activity index, BASFI=Bath ankylosing spondylitis functional index, BASMI=Bath ankylosing spondylitis Metrology Index, CRP=C-reactive protein, ESR=erythrocyte sedimentation rate, FACIT-Fatigue=functional assessment of chronic illness therapy – fatigue, [REDACTED] MRI=magnetic resonance imaging, PR= partial remission, SF-36=Short form health survey, SOC=standard-of-care, VAS=visual analog scale

3 Study design

This is a randomized, parallel-group, open-label, multicenter study in patients with active axSpA. The aim of the study is to demonstrate that the efficacy of a T2T approach (with secukinumab as a first-line biologic) is superior to a SOC approach in terms of achieving strong clinical efficacy in patients with active axSpA who are naïve to biological therapy and who have an inadequate response to prior NSAID treatment. The study will include an 8-week Screening period, a 36-week treatment period, and a 20-week safety follow-up period. Neither investigators nor patients will be blinded. The primary endpoint is the percentage of patients achieving an ASAS40 response at Week 24. At Baseline, patients will be randomized equally to one of 2 treatment groups (T2T or SOC) as shown in [Figure 3-1](#):

Figure 3-1 Study design

Patients will be evaluated every 12 weeks from Baseline up to Week 36. Safety evaluations will be included in the regular visits; in addition, a safety follow-up visit will be performed 20 weeks after the last study visit (i.e. Week 36) and will take place at Week 56 for patients completing the study according to the protocol. In addition, patients in the T2T arm will be seen for safety monitoring at Visit 4 (Week 4) and Visit 5 (Week 8). Patients who prematurely discontinue completely from the study for any reason should return for the final visit to conduct the Week 36 assessments (4 weeks after the last study treatment administration), then also return after an additional 20 weeks for a final follow-up visit, corresponding to Week 56 assessments.

T2T group (n = 150)

Starting from Baseline, patients will be treated with secukinumab 150 mg subcutaneous (s.c.) weekly until Week 4 and then at Week 8.

At Week 12:

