4.1.1 Bias-reducing measures

In order to avoid selection bias in this study, patients will be randomized to the two treatment groups. All study sites will be provided with a set of sealed allocation cards. At the Randomization Visit, the investigator will assign each patient who meets the study eligibility criteria to the lowest available randomization number, open the corresponding treatment allocation card and treat the patient with the treatment noted on the card (i.e. T2T treatment or SOC treatment).

As blinding of site personnel and patients is not possible in practice for the chosen study design, there is a risk of performance bias. Performance bias refers to systematic differences between groups in the care that is provided. To ensure the control of performance bias, the assessments (timing of study visits, patient and physician disease activity checks and outcomes, etc.) in both treatment groups are identical, with the exception of additional blood samples at Week 4 and Week 8, which are required for secukinumab as per German Society of Rheumatology (Deutsche Gesellschaft für Rheumatologie e.V. - DGRh) recommendations (Table 8-1).

The treatment in T2T arm and in SOC arm is described in detail in Section 6.1. The treatment in the SOC arm will follow the clinical routine of the investigator and should be in accordance with current guidelines for treatment of axSpA ([van der Heijde et al 2017](#)). All investigators will be trained on the specifics of treating patients that receive the standard-of-care regimen. In addition, current EULAR guidelines for treatment of axSpA will be provided to all study sites. The clinical monitoring team, who are educated in current treatment guidelines, will check site adherence to these guidelines during the regular monitoring visits. Reasons for non-adherence will be investigated and documented properly. Furthermore, the necessity of adherence to guidelines will be emphasized to investigators.

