'S' designates assessments which are recorded in source documentation only.

'C' designates centrally analyzed laboratory or questionnaire results which are entered into the database by a central laboratory or by data management; for these assessments, only the date of the assessment needs to be entered into the eCRF by the site staff.

^a only in case the patient has been seen for the optional visit at site, else, the information will be obtained at the next obligatory site visit.

¹ As according to the DGRh recommendation, for patients treated with secukinumab following laboratory parameters should be evaluated at the therapy week 4 and 8:m ESR, hsCRP, full blood count, ALT, Creatinine.

² Eligibility and relevant medical history assessments are conducted at SV1, SV2 and Baseline but recorded only once in the eCRF.

³ The last available X-ray and/or MRI of the sacroiliac joints done in order to confirm/revise the axSpA diagnosis should be uploaded into the central reading platform.

⁴ If patients do not have a chest X-ray available within 3 months of Screening, an X-ray should be performed after it is certain the patient meets inclusion/exclusion criteria in order to minimize unnecessary exposure to X-ray radiation. In some sites selected by Novartis, the X-ray assessment may be replaced by chest MRI assessment.

⁵ MRIs performed up to 3 months prior to Screening will be accepted; MRI should be performed during Screening only if patient's quick CRP test is negative (i.e. ≤ 5 mg/L).

⁶ In case an actual (not older than 3 months) MRI image of sacroiliac joints (and spine) is available, it should be uploaded into the central reading platform. If a patient has a negative quick CRP (i.e. ≤ 5 mg/L) at Screening, a MRI of the sacroiliac joints and spine must be performed during the Screening to ensure the presence of objective signs of inflammation of the sacroiliac joint and the MRI should be uploaded into the central reading platform.

⁷ In case the patient has been already tested for HLA-B27 antigen, the result of the test will be entered in the eCRF and no central re-test will be performed.

⁹ All questionnaires will be completed at the scheduled study visit prior to the patient seeing the investigator for any clinical assessment or evaluation.

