10.1 Definition of adverse events and reporting requirements

10.1.1 Adverse events

An AE is any untoward medical occurrence (e.g. any unfavorable and unintended sign [including abnormal laboratory findings], symptom or disease) in a patient or clinical investigation patient after providing written informed consent for participation in the study. Therefore, an AE may or may not be temporally or causally associated with the use of a medicinal (investigational) product. In addition, all reports of intentional misuse and abuse of the study treatment are also considered an AE irrespective if a clinical event has occurred. See [Section 10.1.5](#) for an overview of the reporting requirements.

The investigator has the responsibility for managing the safety of individual patient and identifying AEs.

Novartis qualified medical personnel will be readily available to advise on trial related medical questions or problems.

The occurrence of AEs must be sought by non-directive questioning of the patient at each visit during the study. Adverse events also may be detected when they are volunteered by the patient during or between visits or through physical examination finding, laboratory test finding, or other assessments.

Adverse events must be recorded under the signs, symptoms or diagnosis associated with them, accompanied by the following information (as far as possible) (if the event is serious refer to [Section 10.1.3](#)):

1. The severity grade:
 - Mild: Usually transient in nature and generally not interfering with normal activities
 - Moderate: Sufficiently discomforting to interfere with normal activities
 - Severe: Prevents normal activities
2. Its relationship to the investigational treatment and other treatment. If the event is due to lack of efficacy or progression of underlying illness (i.e. progression of the study indication) the assessment of causality will usually be 'not suspected.' The rationale for this guidance is that the symptoms of a lack of efficacy or progression of underlying illness are not caused by the trial drug, they happen in spite of its administration and/or both lack of efficacy and progression of underlying disease can only be evaluated meaningfully by an analysis of cohorts, not on a single patient.
3. Its duration (start and end dates) or if the event is ongoing an outcome of not recovered/not resolved must be reported.

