2.8.1 Adverse events (AEs)

All information obtained on AEs will be displayed by treatment group and subject. Summary tables for AEs will summarize only on-treatment events, with a start date during the on-treatment period (see [Section 2.1.1](#) for definition of on-treatment period).

The count of treatment-emergent AEs, number (and percentage) of subjects with treatment-emergent AEs (defined as events started after the first dose of study treatment or events present prior to start of study treatment but increased in severity based on PT) will be summarized in the following ways:

- By treatment, primary system organ class and PT.
- By treatment, primary system organ class, PT and maximum severity.

Adverse events in the T2T arm will be summarized by 3 groups (secukinumab 150 mg, secukinumab 300 mg and adalimumab 40 mg).

Adverse events occurring in the SOC arm for patients treated with any of the following: secukinumab 150 mg, secukinumab 300 mg, adalimumab 40 mg and other will also be summarized under a separate SOC page.

Separate summaries will be provided for study treatment related AEs, death, SAEs, other significant AEs action taken leading to study drug withdrawn and AEs leading to dose adjustment (dose increase, dose reduce).

Adverse events will be summarized by presenting, for each treatment group, the number and percentage of patients having any AE, having an AE in each primary system organ class and having each individual AE (PT). Summaries will also be presented for AEs by severity and for study treatment related AEs. If a patient reported more than one AE with the same PT, the AE with the greatest severity will be presented. System organ classes will be presented in alphabetical order, preferred terms will be sorted within system organ class in descending frequency of AEs in the T2T treatment group. If a subjects reported more than one AE within the same primary system organ class, the patient will be counted only once with the greatest severity at the system organ class level, where applicable.

For the legal requirements of ClinicalTrials.gov and EudraCT, 2 required tables on treatment emergent AEs which are not serious adverse events with an incidence greater than 5% and on treatment emergent SAEs and SAEs suspected to be related to study treatment will be provided by system organ class and PT on the safety set population.

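### The by-drug AE table for the T2T arm is not like-for-like: obligatory AE collection is densest in Weeks 0–12, when every T2T patient is on 150 mg

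*SAP*

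**What the plan says.** **Analysis.** SAP 2.8.1 states: "Adverse events in the T2T arm will be summarized by 3 groups (secukinumab 150 mg, secukinumab 300 mg and adalimumab 40 mg". The measure is "the number and percentage of patients having any AE, having an AE in each primary system organ class and having each individual AE (PT". That section plans no test and gives no split by period, no exposure adjustment and no rule for assigning an event to one of the three groups. Treatment Periods 1 to 3 are already defined in SAP 2.1.1, and SAP 2.4.1 uses treatment periods to count injections.

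**Collection.** Protocol 10.1.1: "The occurrence of AEs must be sought by non-directive questioning of the patient at each visit during the study". It adds: "Adverse events also may be detected when they are volunteered by the patient during or between visits". Protocol 3 sets the schedule: "Patients will be evaluated every 12 weeks from Baseline up to Week 36", and "In addition, patients in the T2T arm will be seen for safety monitoring at Visit 4 (Week 4) and Visit 5 (Week 8". SOC patients are seen 12-weekly, or more often if clinically indicated. Footnote 1 to Table 8-1 adds laboratory work: "for patients treated with secukinumab following laboratory parameters should be evaluated at the therapy week 4 and 8" (ESR, hsCRP, full blood count, ALT, creatinine). Protocol 4.1.1 calls assessments in the two arms identical, "with the exception of additional blood samples at Week 4 and Week 8". It does not mention that those are also visits at which AEs are asked about.

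**Treatment path (Protocol 3, Table 8-2).** All T2T patients start on 150 mg. Week 12 responders stay on it to Week 32, and non-responders move to 300 mg. Those still not responding at Week 24 move to adalimumab. Patients on 150 mg who lose response at Week 24 can move to 300 mg.

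**Other contacts (Protocol 6.7.2).** Injections outside mandatory visits may be given at home or at optional site visits. Home-injecting patients should contact the site before injecting if they have an AE.

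**The concern.** The number and percentage of patients with treatment-emergent AEs is the endpoint for the safety objective (Protocol Table 2-1, SAP Table 1-1). The three T2T columns will be read side by side even though no test is planned.

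The dense part of the schedule falls only on 150 mg, because 300 mg starts at Week 12 and adalimumab at Week 24. Minor, short-lived events may be remembered better over 4 weeks than over 12.

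Part of the effect needs no recall assumption. Laboratory abnormalities can qualify as AEs (Protocol 10.1.1), and Protocol 4.4 describes most neutropenia as mild and transient. An abnormality that has resolved by the next sampling cannot be reported by the patient later.

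The same two visits separate T2T from SOC in the first 12 weeks.

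**Working it through.** The plan states no AE rate or detection rate, so there is no figure of its own to reproduce.

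**1. Scheduled contacts per 12 weeks** (Protocol 3, Tables 8-1 and 8-2)

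| T2T segment | Home injection (obligatory visits only) | All injections at site |
|---|---|---|
| 150 mg, Weeks 0–12 | 3 (4, 8, 12) | 6 (1, 2, 3, 4, 8, 12) |
| 150 mg, after Week 12 | 1 | 3 |
| 300 mg | 1 | 3 |
| Adalimumab, Weeks 24–36 | 1 | 6 (26, 28, 30, 32, 34, 36) |

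SOC has 1 per 12 weeks as a minimum.

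**2. Illustrative capture model.** Assumptions, none from the documents: a constant true AE rate, equal on all drugs, and a chance of reporting at the next visit that halves every h weeks. Mean capture over a visit gap of g weeks is c(g) = (1 − e^(−kg))/(kg), with k = ln 2/h.

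For pooling, half the patients stay on 150 mg to Week 36. This follows the roughly 50% non-response at Week 12 in SAP 3 and ignores later escape. Mean 150 mg time per patient is then 12 dense weeks plus 0.5 × 24 = 12 sparse weeks, so pooled capture is the average of the two.

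Home injection:

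| h (weeks) | c(4) | c(12) | Pooled 150 mg = (c(4) + c(12))/2 | Ratio to 300 mg or adalimumab |
|---|---|---|---|---|
| 8 | 0.845 | 0.622 | 0.733 | 1.18 |
| 12 | 0.893 | 0.721 | 0.807 | 1.12 |
| 26 | 0.949 | 0.856 | 0.902 | 1.05 |
| no loss | 1 | 1 | 1 | 1.00 |

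All injections at site. Weeks 0–12 capture is [4c(1) + 8c(4)]/12; later secukinumab is c(4); adalimumab is c(2):

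| h (weeks) | Pooled 150 mg | 300 mg | Adalimumab | 150/300 | 150/adalimumab |
|---|---|---|---|---|---|
| 8 | 0.864 | 0.845 | 0.918 | 1.02 | 0.94 |
| 12 | 0.906 | 0.893 | 0.944 | 1.01 | 0.96 |
| 26 | 0.955 | 0.949 | 0.974 | 1.01 | 0.98 |

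**3. Exposure alone, perfect capture.** Share with at least one AE is 1 − e^(−rw/52) for w weeks at r events per patient-year. At an assumed r = 2, this gives 37% for 12 weeks, 60% for 24 weeks and 75% for 36 weeks. The 150 mg column (half 12 weeks, half 36 weeks) shows 0.5 × 37% + 0.5 × 75% = 56%, against 37% for 12 weeks of 300 mg or adalimumab. For r = 1 to 3 the ranges are 35% to 69% for 150 mg, 21% to 50% for 12 weeks of either other drug, and 37% to 75% for 24 weeks of 300 mg.

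**4. T2T against SOC over 36 weeks**, with home injection and no extra SOC visits: (12c(4) + 24c(12))/(36c(12)).
- h = 8: (10.14 + 14.93)/22.39 = 1.12
- h = 12: (10.72 + 17.30)/25.96 = 1.08
- h = 26: (11.39 + 20.54)/30.82 = 1.04

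The laboratory effect is not quantified. The documents give no rate for it.

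**The case against.** The strongest reply is that fewer visits do not remove time at risk. Later visits look back over the whole interval, AEs can be volunteered in between, and the request to contact the site before a home injection recurs 4-weekly on secukinumab and 2-weekly on adalimumab. With no recall loss the ratio is 1.00, and nothing in the documents supports any particular half-life. This stands as to size. It does not make the schedules equal, and volunteered reports do not replace active questioning or a blood test.

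A reader might infer that the table inflates 150 mg by construction, or hides a dose-related excess at 300 mg. The documents do not support that. Week 12 responders remain on 150 mg under the sparse schedule, so dense collection is not fully tied to drug. Comparing only Weeks 0–12 on 150 mg with later drugs would give ratios of 1.36, 1.24 and 1.11 at half-lives of 8, 12 and 26 weeks, but the SAP does not tabulate that contrast. Site visits nearly remove the difference from 300 mg and can reverse it against adalimumab.

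Three further points stand. The table is descriptive. SOC patients may be seen more often than 12-weekly, so the T2T/SOC ratios in step 4 rest on the minimum SOC schedule. By-period columns bring their own problem: in Periods 2 and 3 drug depends on response, so 150 mg against 300 mg sets Week 12 responders largely against non-responders.

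**Conclusion.** The point holds as one about comparability. Obligatory questioning and laboratory sampling are denser in Weeks 0–12, all of it on 150 mg. SAP 2.8.1 pools this with later time as crude percentages, and the columns also differ in exposure.

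The collection effect has no known size. The 1.05 to 1.18 range rests on assumed half-lives of 8 to 26 weeks, home injection, equal true rates and half the patients staying on 150 mg. Its direction against adalimumab depends on how many patients choose site visits. Under the assumed AE rates, unequal exposure moves the crude percentages more than this does. Serious events should be little affected by recall.

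One limit remains: the AE row of Table 8-1 is not in the text available here, so questioning at every visit rests on Protocol 10.1.1.

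**What to change.** In SAP 2.8.1:

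- Present AEs also by the treatment periods of SAP 2.1.1, with exposure time for each drug in each period.
- Show T2T against SOC for Weeks 12–36 next to the overall table. The obligatory schedule is the same in both arms over that span.
- Footnote the two extra obligatory T2T visits with their laboratory tests, and the optional site visits.
- State that the 150 mg, 300 mg and adalimumab columns within Periods 2 and 3 are descriptive, because drug is assigned by response status.

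The cost is a paragraph of SAP text and a few extra outputs from data already collected, with no change to trial conduct. The downside is fewer events in each table.

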
• To demonstrate that the efficacy of the T2T approach (with secukinumab as first-line biologic) is superior to the SOC approach based on the percentage of subjects achieving ASAS 20% response (ASAS20), ASAS partial remission (PR), and Bath Ankylosing Spondylitis Disease Activity Index 50% response (BASDAI50) responses at Week 12 and Week 24.• To demonstrate that the T2T approach (with secukinumab as first-line biologic) is superior to the SOC approach in terms of improvement of disease activity, function, axial mobility, and quality of life measures at Week 12 and Week 24 as compared to Baseline according to:
◦ BASDAI◦ ASDAS◦ C-Reactive Protein (CRP) and Erythrocyte Sedimentation Rate (ESR)◦ Bath Ankylosing Spondylitis Functional Index (BASFI)◦ Bath ankylosing spondylitis metrology index (BASMI) and chest expansion◦ Global assessment of disease activity (patient/physician) and general pain on Visual Analog Scale (VAS)◦ ASAS health index (ASAS-HI)◦ Short Form Health Survey (SF-36)◦ Ankylosing Spondylitis Quality of Life (ASQoL)◦ Functional Assessment of Chronic Illness Therapy - Fatigue (FACIT-Fatigue).• To demonstrate overall safety and tolerability of secukinumab.	
• Percentage of subjects achieving ASAS20, ASAS PR, BASDAI50 responses at Week 12 and Week 24.• Improvement of disease activity, function, axial mobility, and quality of life measures at Week 12 and Week 24 as compared to Baseline according to:
◦ BASDAI◦ ASDAS◦ CRP and ESR◦ BASFI◦ BASMI and chest expansion◦ Global assessment of disease activity (patient/physician) and general pain on the VAS◦ ASAS-HI◦ SF-36◦ ASQoL◦ FACIT-Fatigue• The number (and percentage) of patients with treatment-emergent adverse events (AEs).

2 Statistical methods

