2.1.1 General definitions

Study treatment: Study treatment refers to:

1. Investigational treatment Treat to Target (T2T) = secukinumab 150 mg and/or 300 mg and/or adalimumab biosimilar 40 mg (GP2017)
2. Standard of Care (SOC) treatment up to the maximum recommended dose at the discretion of the investigator

The **treatment phase** is defined as the period from randomization until end of the last treatment period with treatment periods defined as:

- Period 1: date of randomization until day before visit Week 12
- Period 2: date of visit Week 12 until day before visit Week 24

- Period 3: date of visit Week 24 until day before visit Week 36

The following exceptions are made to these definitions:

- If visit Week 12 or 24 is missing but the next visit is documented, the visit date is interpolated in the middle between the earlier and the later visit.
- End dates of period 1, 2, 3: If no further visit was performed during the treatment phase after start of the period, the end date is set to the documented end of treatment date or to the period start date, if no treatment was applied in this period.
- End date of period 3: If the documented end of treatment date is on visit Week 36 date or later, the end date of period 3 is set to the end of treatment date.
- Treat-to-Target group: If treatment was not applied at visit Week 12 or 24, or the last dose of the previous period was still applied on the date of visit, the start date of period 2 resp. 3 is set to the date of first dose in this period. Cases where the last dose of the previous period was still applied on the visit date are identified by the same dose as in the previous period applied on the visit date, but treatment was switched at the first dose after the visit.

Treat-to-Target regimen

Starting from Baseline, subject will be treated with secukinumab 150 mg subcutaneous (s.c.) weekly until Week 4 and then at Week 8.

At Week 12

- If the subject achieves and maintains an ASDAS clinically important improvement (i.e. change from Baseline in ASDAS ≥ 1.1 indicating subjects is a responder), then the subject will continue with secukinumab 150 mg s.c. every 4 weeks up to Week 32.
- If the subject did not achieve ASDAS clinically important improvement (i.e. non-responder) then the subject will receive an escalated dose of secukinumab 300 mg s.c. every 4 weeks until Week 20.

At Week 24

Subjects who are receiving secukinumab 300 mg and

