- Achieves ASDAS clinically important improvement (i.e. responder) will continue with secukinumab 300 mg s.c. every 4 weeks up to Week 32.
- Do not achieve ASDAS clinically important improvement (i.e. non-responder), will be switched to adalimumab biosimilar (GP2017) 40 mg s.c. every 2 weeks until Week 34.

Escape arm

- Subjects who are receiving 150 mg secukinumab (i.e. were responders at Week 12) can be escalated at Week 24 to 300 mg secukinumab every 4 weeks until Week 32 if they experience a loss of response, where loss of response is defined as ASDAS change from Baseline <1.1 .

If the ASDAS measurement is missing at a visit, it is assumed that the planned dose continues for the next treatment period.

Standard of Care Regimen

Patients will receive treatment according to local practice standards by their treating physician following the current treatment recommendations with NSAIDs as the first-choice drug treatment and disease-modifying anti-rheumatic drugs (DMARDs) for patients with active disease because of a lack of response, intolerance, or contraindication to NSAIDs ([van der Heijde et al 2017](#)). Patients will be seen every 12 weeks or more often, if clinically indicated up to Week 36; assessment of the outcome parameters will be performed at Week 12, Week 24 and Week 36.

Study treatment (T2T) start and end date: Study treatment start date is defined as the first date of study drug administration and recorded on the Drug Administration Record (DAR) Electronic Case Report Form (eCRF) page. Similarly, study drug end date is defined as the last date of study drug administration and is recorded on the DAR eCRF page.

SOC treatment start and end date: SOC treatment start date is defined as the first date of any SOC drug for AxSPA treatment after randomization. Similarly, SOC drug end date is inferred as the last date of any SOC drug administration for AxSPA treatment within the treatment phase.

Study day: Study Day 1 is defined as the first day of administration of randomized study treatment. Study day will be calculated as (event date – study drug start date + 1 day) for events that occurred on or after study drug start date (e.g. visit, lab samples, AEs). For events prior to study drug start date (e.g. time since diagnosis), study day will be negative and calculated as (event date – study drug start date).

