Baseline and post-Baseline: Baseline value refers to the value of the last non-missing measurement collected prior to administration of the first dose of study treatment (screening or Baseline visit). A post-Baseline value refers to a measurement taken after the first dose of study treatment.

Change from Baseline: The difference of measure between post-Baseline and Baseline is called change from Baseline.

Percent change from Baseline: The percent change from Baseline will be calculated as below:
 $((\text{post-Baseline value} - \text{Baseline value}) / \text{Baseline value}) * 100$.

On-treatment period: The on-treatment period lasts from the date of first administration of study treatment to 30 days after the date of the last actual administration of any study treatment or end of treatment phase, whichever is later.

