2.4 Treatments (study treatment, rescue medication, concomitant therapies)

2.4.1 Study treatment

Duration of exposure

The number of injections will be summarized by treatment groups, overall and within treatment periods. Duration of exposure to the study treatment will be calculated as the number of days between the first dose date and the last dose date exposed to that treatment over the specified period (expressed as: Duration of exposure = Date of last known dose of study drug – Date of first dose of study drug + 1).

The duration of exposure (in days) to the study treatment by treatment group (T2T, SOC, Other and Overall) will be summarized for the safety set as below

- a continuous variable with the standard descriptive statistics, and
- a categorical variable classified into < 12 weeks, ≥ 12 and < 24 weeks, ≥ 24 and < 36 weeks, ≥ 36 weeks with number and percentage of subjects in each category.
- On-treatment exposure = Date of last known dose of study drug – Date of first dose of study drug + 1 + 30).

Furthermore, the T2T arm will be summarized by treatment (secukinumab 150 mg, secukinumab 300 mg, adalimumab 40 mg). The T2T arm will also be summarized for actual treatment arm.

Similarly, in the SOC arm all medications will be summarized along with their drug class.

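### T2T adverse events are split by drug and dose as counts and crude percentages, with no exposure-adjusted rate, although planned time on each drug differs

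*SAP*

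**What the plan says.** SAP 2.8.1 divides T2T adverse events by drug and dose: "Adverse events in the T2T arm will be summarized by 3 groups (secukinumab 150 mg, secukinumab 300 mg and adalimumab 40 mg"). The measures are "The count of treatment-emergent AEs, number (and percentage) of subjects with treatment-emergent AEs" and, "for each treatment group, the number and percentage of patients having any AE". No rate per patient-time is mentioned.

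SAP 2.1.1 shows that the three groups are successive regimens. Everyone in T2T starts on 150 mg. Week 12 non-responders move to 300 mg. Those who still fail at Week 24 "will be switched to adalimumab biosimilar (GP2017) 40 mg s.c. every 2 weeks until Week 34". Week 12 responders who lose response by Week 24 can escalate to 300 mg.

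The other relevant rules are these:

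- **Treatment received (SAP 2.2, Safety Set):** defined by the first dose. That is 150 mg for every T2T patient who follows the regimen, so this rule cannot fill the 300 mg and adalimumab columns.
- **Treatment periods (SAP 2.1.1):** in the T2T exceptions, "the start date of period 2 resp. 3 is set to the date of first dose in this period". Adverse events are not tied to these periods.
- **On-treatment period (SAP 2.1.1):** one window per patient, ending "30 days after the date of the last actual administration of any study treatment or end of treatment phase, whichever is later".
- **Exposure (SAP 2.4.1):** "Furthermore, the T2T arm will be summarized by treatment (secukinumab 150 mg, secukinumab 300 mg, adalimumab 40 mg"). A further T2T view, by actual arm, is mentioned but not defined.

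The safety objective in SAP 1.2 is "To demonstrate overall safety and tolerability of secukinumab".

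**The concern.** A crude percentage rises with time at risk. When columns differ in planned follow-up, a column with less time shows a lower percentage even if the drugs carry the same risk. Here the treatment algorithm itself sets the difference. Adalimumab starts only at Week 24, while Week 12 responders can stay on 150 mg for the whole treatment phase.

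Without a stated assignment rule, the same data can also produce materially different tables.

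The safety objective concerns secukinumab, but the SAP text describes no T2T column that pools both secukinumab doses and leaves adalimumab out. What is at stake is how the descriptive safety tables are read. No efficacy result is involved.

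**Working it through.** The documents give no time at risk per drug and no AE rate, so there is no stated figure to reproduce.

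**Inputs from the documents.** Scheduled days are Week 12 = Day 85 and Week 24 = Day 169 (SAP 2.1.2). The last secukinumab dose is at Week 32 (Day 225) and the last adalimumab dose at Week 34 (Day 239). The on-treatment period adds 30 days, giving Day 255 and Day 269. Both fall after the scheduled Week 36 day (253), so the 30-day rule sets the end. Week 12 non-response is p = 0.5 (SAP section 3). There are 150 T2T patients.

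**Assumptions.** Events are assigned to the drug in use at onset. Denominators are patients ever treated with that drug. A constant hazard r per week is equal on all drugs. Week 24 failure on 300 mg is f = 0.3 to 0.7. The base case has full adherence and no escape.

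**Days at risk per patient**

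- 150 mg: 84 (Week 12 non-responder) or 255 (responder)
- 300 mg: 84 (fails at Week 24) or 171
- adalimumab: 269 − 168 = 101

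**Mean weeks**

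- 150 mg: (0.5 × 84 + 0.5 × 255)/7 = 24.2
- 300 mg: 20.7, 18.2 and 15.7 for f = 0.3, 0.5 and 0.7
- adalimumab: 101/7 = 14.4

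**Expected percentage with at least one event.** With F(d) = 1 − exp(−r·d/7):

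- 150 mg = pF(84) + (1 − p)F(255)
- 300 mg = fF(84) + (1 − f)F(171)
- adalimumab = F(101)

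| r per week | 150 mg | 300 mg (f = 0.3 to 0.7) | adalimumab |
|---|---|---|---|
| 0.01 | 20.9% | 18.6% to 14.4% | 13.4% |
| 0.025 | 42.8% | 39.8% to 31.9% | 30.3% |
| 0.05 | 64.5% | 62.9% to 52.7% | 51.4% |

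For r = 0.025, F(84) = 25.9% and F(255) = 59.8%, so 150 mg is 0.5 × 25.9 + 0.5 × 59.8 = 42.8%.

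**Sensitivity at r = 0.025, 150 mg versus adalimumab**

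- Non-response of 40%, 60% or 70%: 46.2%, 39.5% or 36.1% versus 30.3%. The order reverses only above 87% non-response.
- 20% dropout by Day 255: 39.8% versus 29.1%.
- 20% of Week 12 responders escaping at Week 24: 41.4% versus 30.3%.
- Hazard halved after the first 12 weeks on each drug: 36% versus 28%. Cut to a quarter: 31% versus 27%. Cut to zero: no gap.
- Patients grouped by final sequence over their whole on-treatment time: F(255) = 59.8% for the secukinumab-only sequences versus F(269) = 61.7% for those ending on adalimumab. The gap disappears and slightly reverses.

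**300 mg versus 150 mg.** 300 mg is lower in the table above. At r = 0.025 the order reverses above 59%, 71% or 82% Week 12 non-response, for f = 0.3, 0.5 or 0.7.

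**What a rate would do.** At equal risk of 0.025 per week, the expected rate is 0.025 × 365.25/7 × 100 = 130 per 100 patient-years in every column.

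**Precision on adalimumab.** Patients reaching it: 150 × 0.5 × f = 22.5 to 52.5. Planned time: 22.5 × 101/365.25 = 6.2 to 52.5 × 101/365.25 = 14.5 patient-years. Expected patients with a first event: 22.5 × 0.303 = 6.8 to 52.5 × 0.303 = 15.9. The Poisson 95% interval around 130 is then about 52 to 271, or 74 to 212.

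**Adalimumab share of T2T on-treatment time.** 2272.5/38565 = 5.9% (f = 0.3) to 5302.5/38985 = 13.6% (f = 0.7).

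**The case against.** The strongest objection is that the SAP does not fix the assignment rule, so the direction of any distortion is not established. Three groups could also mean three final sequences, and the undefined actual-arm view in SAP 2.4.1 leaves room for that. This stands, and it is why the conclusion is conditional. It does not rescue the table. Grouping by final sequence removes the time imbalance only by counting events that occurred on secukinumab under adalimumab.

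Second, SAP section 1 places table shells and programming specifications in separate documents, which may hold the rule, the denominator or a pooled secukinumab column. That is possible. The SAP text should still state or cite them.

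Third, the prespecified safety endpoint is the number and percentage of patients with treatment-emergent AEs, and no comparison between drugs within T2T is planned. Both are true. The remedy therefore adds to the percentages and does not replace them.

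Fourth, exposure by drug is reported, so a reader could form a rate. But the first duration in SAP 2.4.1 runs from first to last dose: 57 or 225 days on 150 mg (mean 141) and 71 on adalimumab. Events count over means of 169.5 and 101 days. At equal risk, a rate built on that duration would be (101/71)/(169.5/141) = 1.18 times as high for adalimumab as for 150 mg. SAP 2.4.1 also lists a version with 30 days added, which largely fixes this, but it is not tied to the AE columns.

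Finally, the size depends on an assumed rate and a constant hazard. That stands. With risk concentrated early on each drug, the gap is smaller.

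**Conclusion.** The point holds in conditional form and is minor. SAP 2.8.1 presents sequential regimens with unequal planned time at risk as crude percentages. With assignment by drug at onset (the likely reading, but not stated), ever-treated denominators and a roughly constant hazard, adalimumab shows a lower percentage than secukinumab 150 mg at equal true risk. The illustration is 30% versus 43% at 0.025 per week. Across rates of 0.01 to 0.05 per week it runs from 13% versus 21% to 51% versus 64%.

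A reader might infer that the plan is bound to make adalimumab look safer. The documents do not support that, because they state neither the assignment rule nor the denominator, and final-sequence grouping removes the gap. Nor do they support a fixed order between 300 mg and 150 mg, which depends on the response rates at Weeks 12 and 24. The randomised T2T versus standard-of-care comparison is not affected.

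**What to change.** In SAP 2.8.1:

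1. Assign each treatment-emergent AE to the drug and dose last taken before onset, using the period start dates in SAP 2.1.1. Use as denominator the patients given at least one dose of that drug and dose.
2. For any AE and any SAE only, add the number of patients with a first event per 100 patient-years on that drug and dose. Count time to the first event or to the end of on-treatment time on that drug. Give no such rates by system organ class or preferred term.
3. Add an 'any secukinumab' column for the secukinumab safety objective.

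The cost is a few lines of SAP text, two rate rows and one column, from onset and dosing dates already collected. The downside is precision: adalimumab has only about 6 to 15 planned patient-years, so its interval will be wide. The rate corrects for unequal time only. It does not correct for selection by non-response, calendar order or carry-over from the previous drug, and a footnote should say so.
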